STUDY OBJECTIVES	 Characterise longitudinal trends of patient-reported Forced Vital Capacity (FVC) and outcome measures in patients with idiopathic pulmonary fibrosis (IPF). Determine the correlation between patient-reported FVC and outcome measures with clinic-observed measurements. Assess if longitudinal trends in patient-reported FVC predict clinical outcomes. Characterise the acceptability and utility of the patientMpower app from patient and healthcare professional perspectives.
METHODOLOGY	Prospective, open-label, single-arm observational study. Usual care for all patients throughout study.
NUMBER OF SUBJECTS	Total randomised: target = 25

	Actual intention-to-treat: 21. Treated dataset: 20
DIAGNOSIS	Confirmed diagnosis of IPF
MAIN CRITERIA FOR INCLUSION	Age ≥18 years, daily access to smartphone or tablet device, email address, demonstrated understanding of use of patientMpower app and home spirometry, written informed consent
TEST PRODUCT	patientMpower intervention (defined as patientMpower app + home spirometer) used daily + usual care
COMPARATOR PRODUCT	None
DURATION OF OBSERVATION	Sixteen ± eight weeks (corresponding to interval between usual care visits)
END OF STUDY DEFINITION	Date of first usual care visit after baseline visit (typically at sixteen ± eight weeks)
PRIMARY ENDPOINTS	Trend of patient-measured FVC over time. Degree of correlation between patient- measured FVC with clinic- observed measures
SECONDARY ENDPOINTS	Trends of patient-reported outcomes over time. Degree of correlation between patient- reported outcomes with clinic-observed measures. Patient and healthcare professional perspectives on preference for and difficulty using the app and helpfulness in managing IPF. Impact of app on patient self- management of IPF and daily living.
INTERIM ANALYSIS	Analysis of data up to 18 October 2019 to prepare abstract for American Thoracic Society 2020
STATISTICAL METHODS	Descriptive statistics tables prepared for all endpoints

FLOW CHARTS

Flow chart 2: Assessments during observation period

	Baseline (clinic visit)	Install app & pair spirometer	*Daily (patient - reported)	16 (±8) weeks End study (clinic visit) ¹
	day 0	day 0-2	daily	week 16
				(approx.)
Informed consent	Х			
Start of study	Х			
Spirometry, assess dyspnoea	Х			X
Demographic data (include IPF history & medicines history ³)	Х			
Patient training &	Х			
encouragement				
Installation of		Х		
patientMpower app & pair				
spirometer				

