1.3 Dates of study conduct

The first patient gave informed consent and entered the study on 28 November 2018. In-clinic visits were cancelled at the study centre in March 2020 because of the COVID19 pandemic and the last two patients did not have end-of-study clinic visits. Data for all patients who had completed the study by 30 April 2020 and for the two patients who were still on study on 30 April 2020 are included in this analysis.

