Correlation between clinic-observed and patient-recorded FVC was assessed as follows. The means of the first seven days of patient-recorded FVC after baseline and of the last seven days of patient-recorded FVC before the end-of-study clinic visit were calculated. Outlier values were detected by inferring a rolling average of the patient-recorded data using the EWMA algorithm and removing values far away from this average, taking into account heightened uncertainty of the average during periods of poor engagement. Outlier values were excluded and the means of spirometry values within the first seven days after the baseline clinical FVC (mean baseline spirometry) and the last seven days before their end-of-study clinical FVC (mean endpoint spirometry) were calculated. Patients without a single spirometry value in either 7 day window were excluded.

For both baseline and end-of-study, the correlation between in-clinic FVC and patient-recorded FVC was calculated by randomly sampling from the data with replacement and calculating the usual Pearson correlation coefficient. This process was repeated 1000 times, giving an empirical distribution for correlation. This process is known as bootstrapping [7]. The mean of this distribution is the inferred correlation, and the standard error is the standard deviation of this distribution divided by the square root of 1000.

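### SAP 5.3 divides the bootstrap standard deviation by √1000 and calls the result the standard error, which understates the uncertainty of the home-versus-clinic FVC correlation 31.6-fold

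*SAP*

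**What the plan says.** SAP 5.3 (Planned analysis) correlates in-clinic FVC with the mean of home FVC over a seven-day window, once at baseline and once at end of study. The method is "randomly sampling from the data with replacement and calculating the usual Pearson correlation coefficient". It continues: "This process was repeated 1000 times, giving an empirical distribution for correlation". Two summaries of that distribution are then defined. The estimate: "The mean of this distribution is the inferred correlation". Its precision: "the standard error is the standard deviation of this distribution divided by the square root of 1000".

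The SAP does not describe this second quantity as simulation error, and its text gives no confidence interval for the correlation. The SAP synopsis lists, under primary endpoints, "Degree of correlation between patient- measured FVC with clinic- observed measures"; the protocol synopsis does the same.

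**The concern.** The bootstrap imitates repeating the study with new patients. The spread of the resampled correlations therefore estimates how far r would vary from one sample of patients to another, which is what a standard error is. Dividing that spread by the square root of the number of resamples answers a different question: how precisely the computer has located the mean of the bootstrap distribution for this one dataset. That can be made as small as one likes by running the program longer.

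No hypothesis is tested and the sample size was chosen arbitrarily (SAP 5.2 and 5.5), so the estimate and its precision are the result. As written, a correlation from at most 20 patients would be published with an error close to zero. Readers would take home spirometry to have been shown to track clinic spirometry far more precisely than the data allow. Anyone setting the baseline and end-of-study correlations side by side could read chance differences as real.

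**Working it through.** **Inputs from the documents**
- Resamples: B = 1000 (SAP 5.3).
- Patients: the SAP synopsis gives "Treated dataset: 20", an upper limit at baseline.
- End of study: SAP 1.3 says "the last two patients did not have end-of-study clinic visits". If both were in the treated dataset, which the SAP does not say, the upper limit is 20 − 2 = 18.
- Further losses, number not given: "Patients without a single spirometry value in either 7 day window were excluded".

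**Assumed, because the documents give no value:** true correlation ρ from 0.70 to 0.95, bivariate normal data, n = 15, 18 or 20, and patients resampled as pairs. The SAP gives no numerical r or standard error, so there is no plan figure to reproduce.

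**1. The two formulas.** Let SD_boot be the standard deviation of the B resampled correlations.
- Standard error of r: SD_boot.
- Simulation error of the bootstrap mean: SD_boot / √B.

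The SAP reports the second under the name of the first. The ratio is √1000 = 31.62, which depends on none of the assumptions about ρ, n or normality.

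**2. Does the SAP quantity respond to patients or to computing?** One simulated dataset of n = 20 was held fixed and only B was changed:

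| B | SD_boot | SD_boot / √B |
|---|---|---|
| 100 | 0.029 | 0.0029 |
| 1,000 | 0.035 | 0.0011 |
| 10,000 | 0.035 | 0.0003 |
| 100,000 | 0.034 | 0.0001 |

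The spread settles near 0.034 while the SAP quantity keeps shrinking with no new data. Repeating the 1000-resample bootstrap 1000 times on the same data gave a standard deviation of the bootstrap mean of 0.0011. The SAP formula at B = 1000 gives the same value, which confirms that it measures simulation error.

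**3. Size at this study's scale.** The SAP procedure was run on 2000 simulated studies per setting. Coverage is the share of studies in which mean ± 1.96 × (the stated standard error) contains ρ.

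| n | ρ | Actual SD of estimate | Mean SD_boot | SAP standard error | Coverage, SAP | Coverage, SD_boot |
|---|---|---|---|---|---|---|
| 15 | 0.70 | 0.153 | 0.144 | 0.0046 | 5.1% | 88.3% |
| 18 | 0.70 | 0.132 | 0.129 | 0.0041 | 5.3% | 90.3% |
| 18 | 0.80 | 0.098 | 0.095 | 0.0030 | 4.4% | 91.1% |
| 18 | 0.90 | 0.053 | 0.052 | 0.0017 | 5.3% | 91.2% |
| 18 | 0.95 | 0.031 | 0.029 | 0.0009 | 4.5% | 90.4% |
| 20 | 0.90 | 0.051 | 0.050 | 0.0016 | 4.4% | 91.9% |
| 20 | 0.95 | 0.028 | 0.026 | 0.0008 | 5.4% | 90.4% |

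Over all twelve settings run, the actual standard deviation of the estimate was 32.0 to 33.6 times the SAP standard error. It slightly exceeds 31.6 because SD_boot itself runs a little low at these sample sizes.

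**4. One worked case: r = 0.90, n = 18.**
- SAP: the median SD_boot in a separate simulation was 0.047 (the distribution is skewed, so the mean in the table is higher). 0.047 / 31.62 = 0.0015, and 1.96 × 0.0015 = 0.003, so 0.90 ± 0.003.
- Fisher z: atanh(0.90) = 1.472; 1.96 / √(18 − 3) = 0.506; limits 0.966 and 1.978; back-transformed, 0.747 to 0.962.

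**5. Bootstrap mean as the estimate.** In simulation it lay 0.003 to 0.010 below the sample r, which is small against a standard error of about 0.05.

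**The case against.** The formula itself cannot be defended, but the consequences can be argued down.

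- **Primary status.** Protocol 5.1.1.1 and SAP 4.1 name the FVC trend as the primary endpoint and say the correlation is assessed in addition. This stands as an inconsistency with the two synopses. The trend analysis is not touched by the error.
- **Descriptive use.** The plan specifies no confidence interval, no test and no comparison of the two correlations. The coverage figures therefore describe an interval that a reader would build, not one the SAP sets out. That is fair, but a standard error is published so that readers can judge precision in this way.
- **Appendix 1.** SAP 5.3 and 7.1 refer to a separate appendix listing comparisons and tests, which was not available for this review. It may hold another uncertainty measure. That would not make the sentence in SAP 5.3 correct.
- **Sample size.** 20 and 18 are upper limits, because the seven-day window rule removes an unstated number of patients. Fewer patients would generally widen the true uncertainty.
- **Point estimate.** Using the bootstrap mean instead of the sample r is a minor matter and would not justify a change alone.

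The study is a small pilot and no decision rule depends on this number, which limits the harm. None of these points rescues the definition.

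**Conclusion.** The concern holds. The quantity that SAP 5.3 calls the standard error is the simulation error of the bootstrap mean, exactly 1/31.6 of the bootstrap standard error of r. That ratio follows from the SAP's own formula.

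The absolute sizes rest on the assumed n of 15 to 20, ρ of 0.70 to 0.95 and bivariate normality. Across that range the standard error is 0.026 to 0.144, where the SAP formula gives 0.0008 to 0.0046. The error distorts the stated precision and leaves the estimate nearly unchanged. It needs correcting because this is the only precision measure the SAP text defines for an endpoint that both synopses list as primary.

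**What to change.** Replace the two sentences in SAP 5.3 that define the estimate and its standard error with wording such as:

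> The estimate is the sample Pearson correlation. Its standard error is the standard deviation of the 1000 bootstrap correlations, with patients resampled as clinic–home pairs and without division by √1000. The 95% confidence interval runs from the 2.5th to the 97.5th percentile of the bootstrap distribution. The number of patients contributing is reported at baseline and at end of study.

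The percentile interval uses resamples already produced. In simulation at n = 18 and 20 it covered 90–92% rather than 95%, so it is still somewhat narrow. A BCa interval, or a Fisher-z interval if bivariate normality is reasonable, is an acceptable alternative. One should be named and used at both time points.

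The SAP is written in the past tense and reports actual patient numbers, so results may already exist. Any standard error computed with the present formula should be recomputed; multiplying it by 31.62 recovers the bootstrap standard error. Appendix 1 should be checked for the same definition.

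The cost is a short text change and one line of code, with no new data. The reported precision will be visibly worse.

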5.4 Interim analysis

An interim set of data listing was prepared in October 2019 to submit an abstract for American Thoracic Society 2020. There was no formal statistical analysis of these data.

7.1 Variables, data formats, data presentations, statistical comparisons and tests

Listed in NCT03744598 statistics analysis plan appendix 1
